9.3.4 Study Day 15 ± 3 Days

- Concomitant medication assessment
- Clinical laboratory tests: hematology, serum electrolytes and chemistry (including albumin), coagulation parameters, and urinalysis
- Collection of peripheral blood for immunogenicity (serum)
- AE and SAE monitoring

9.3.5 Study Day 21 ± 3 Days

- Concomitant medication assessment
- Clinical laboratory tests: hematology, serum electrolytes and chemistry (including albumin), coagulation parameters, and urinalysis
- Monitoring for changes in visual acuity and color vision
- AE and SAE monitoring

9.3.6 Study Day 28 ± 3 Days, Then Every 7 ± 3 days: Delayed End of Cycle for Toxicity Resolution Only if Required

- Concomitant medication assessment
- ECOG PS
- Physical examination
- Vital signs and weight
- 12-lead ECG
- Clinical laboratory tests: hematology, serum electrolytes and chemistry (including albumin), coagulation parameters, and urinalysis
- Collection of peripheral blood (serum) for immunogenicity

- AE and SAE monitoring

9.4 Cycles 2 – 6

9.4.1 Days 1 – 5 (Up to Day 10 if Infusion(s) Held): Pre-Infusion

- Inpatient admission (Day 1) or treatment at a suitable outpatient facility
- Concomitant medications
- Vital signs and weight
- 12-lead ECG
- Clinical laboratory tests: hematology, serum electrolytes and chemistry (including albumin), coagulation parameters, and urinalysis (Day 1 only for urinalysis)
- Collection of peripheral blood for immunogenicity (infusion 1) immediately prior to the start of the infusion
- AE and SAE monitoring
- Diphenhydramine 50 mg IV 60 minutes prior to infusion
- Acetaminophen 650 mg PO 60 minutes prior to infusion
- Methylprednisolone 50 mg IV (or an equivalent dose of another corticosteroid) 60 minutes prior to infusion
- Ranitidine 50 mg IV (or an equivalent doses of another H₂-histamine antagonist) 60 minutes prior to infusion

9.4.2 Days 1 – 5 (Up to Day 10 if Infusion(s) Held): Infusion

- 12-lead ECG (Cycle 3 only, infusions 1 and 5) performed at 3 distinct time points (triplicates) within 5 minutes prior to each PK sample collection pre-infusion and 30 and 60 minutes post-infusion (also Cycle 1: see Section 9.3)
- Collection of peripheral blood for PK sampling (Cycle 3 only; infusions 1 and 5) collected pre-infusion, immediately after end of infusion (time recorded), and then 15, 30, 45, 60, 90, 120, 180, and 240 minutes after the completion of the infusion (also cycle 1: see Section 9.3)
- 15-minute IV infusion of SL-401 at required dose
- Vital signs: immediately after completion of infusion and 30, 60, and 240 minutes post-infusion
- Monitoring for at least 4 hours
- AE and SAE monitoring

9.4.3 Day 8 ± 3 Days, or 3 ± 3 Days after Completion of Infusions if Infusion(s) Held

- Concomitant medication assessment
- Clinical laboratory tests: hematology, serum electrolytes and chemistry (including albumin), coagulation parameters, and urinalysis
- AE and SAE monitoring

9.4.4 Day 15 ± 3 Days

- Concomitant medication assessment
- Clinical laboratory tests: hematology, serum electrolytes and chemistry (including albumin), coagulation parameters, and urinalysis
- AE and SAE monitoring

9.4.5 Day 21 ± 3 Days

- Concomitant medication assessment
- Clinical laboratory tests: hematology, serum electrolytes and chemistry (including albumin), coagulation parameters, and urinalysis
- Monitoring for changes in visual acuity and color vision
- AE and SAE monitoring

9.4.6 Day 28 ± 3 Days, Then Every 7 ± 3 days: Delayed End of Cycle for Toxicity Resolution Only if Required

- Concomitant medication assessment
- ECOG PS
- Physical examination
- Vital signs and weight
- 12-lead ECG
- Clinical laboratory tests: hematology, serum electrolytes and chemistry (including albumin), coagulation parameters, and urinalysis
- Collection of peripheral blood for immunogenicity (serum)
- AML remission/response assessment: bone marrow aspiration (+ biopsy) at the end of Cycles 2, 4, and 6, and every 3 months (± 1 month) thereafter through 12 months after start of SL-401 and thereafter at the discretion of the Investigator. Bone marrow (2 mL) will be prioritized for assessment of MRD. Any additional bone marrow (+ biopsy) remaining (~5 mL) will be aliquoted for disease response assessment and in vivo

engraftment studies. CD123 is to be assessed in all bone marrow samples (and, if applicable, tissue samples).

- AE and SAE monitoring

Note: For clinical (i.e., concomitant medications, AE assessment, or physical examination) or laboratory assessments stipulated at both Day 28 of a given cycle and Day 1 of a subsequent cycle, separate Day 1 (pre-infusion) assessments/samples do not need to be obtained if the Day 28 assessment/sample from the prior cycle is obtained no more than 24 hours prior to the first infusion of the next cycle to be given. In that case, the data for the Day 28 assessment/sample may be used both as the Day 28 assessment/sample for the prior cycle as well as the Day 1 (pre-infusion) assessment/sample, avoiding the necessity to conduct redundant assessments or draw 2 blood samples in close proximity.

9.5 End of Treatment

- ECOG PS
- Physical examination
- Vital signs and weight
- Monitoring for changes in visual acuity and color vision
- Bone marrow aspiration (+biopsy)

9.6 Safety Monitoring: Through 30 Days after Last Infusion

- Concomitant medications
- AE and SAE monitoring
- Survival status

9.7 Survival Monitoring: Approximately Every 90 Days after End of Treatment

- Survival status and response/disease progression status (for patients in PR/CR at End of Treatment), continuing until assessments of the primary and secondary objectives are completed for all patients; survival status may be performed by telephone contact.
- Patients who undergo SCT will be followed for the occurrence of VOD as part of survival monitoring.
- A blood sample for immunogenicity studies will be collected at least 16 weeks to up to 20 weeks after the last SL-401 dose.

Table 5: Study Events Schedule for Cycle 1 (Study Day -14 to Study Day 28-35)

Tests and Observations	Study Day -14 to -4	Cycle 1					
		Study Day -1 to 0	Study Days 1-5 (Up to Study Day 10 if Infusion(s) Held)		Study Day 8±3 ⁽ⁿ⁾ , 15±3, and 21±3	Study Day 28±3 ^(o)	Study Day 35±3, Then Every 7±3 days
			SL-401 Treatment				Delayed End of Cycle for Toxicity Resolution Only if Required
Screening	Pre-treatment	Pre-Infusion	Infusion	End of Cycle ^(o)			
Informed consent form	X						
Inclusion/exclusion criteria	X						
Medical history including prior therapy, concomitant medications	X						
Concomitant Medications		X			X	X	X
ECOG performance status	X					X	X
Physical examination	X	X				X	
Pregnancy test ^(a)	X						
Vital signs and weight ^(b)	X	X	X	X		X	X
12-lead ECG ^(c)	X	X	X	X (Infusions 1, 5)		X	X
ECHO or MUGA scan ^(d)	X						
Hematology ^(e)	X	X	X		X	X	X
Serum electrolytes ^(f)	X	X	X		X	X	X
Serum albumin ^(g)	X	X	X		X	X	X
Serum chemistry ^(h)	X	X	X		X	X	X
Coagulation parameters: PT/INR, aPTT	X		X		X	X	X
Urinalysis ⁽ⁱ⁾	X		X (Infusion 1)		X	X	X
Tumor response assessment: Bone marrow aspiration + biopsy ^(j)	X						
Administration of premeds ^(k)			X				
SL-401 administration ^(l)				X			
Pharmacokinetic sampling ^(m)			X (Infusions 1, 5)	X (Infusions 1, 5)			
Immunogenicity sampling			X (Infusion 1)		X (day 15)	X	
Vision assessment	X				X (day 21)		
AE and SAE monitoring			X	X	X	X	X

a Urine or serum pregnancy test must be performed within 1 week prior to treatment in women of childbearing potential.

b Vital signs should be performed after patient is sitting for 3-5 minutes. If during dosing period, vital signs should be taken immediately prior to infusion, immediately after completion of infusion, and 30, 60, and 240 minutes post-infusion.

- c All patients will have a 12-lead ECG performed at the screening visit and pre-treatment visit, as well as Day 28. During the days when patients are undergoing PK sampling (Cycles 1 & 3, infusions 1 and 5), an ECG will be performed at 3 distinct time points (triplicates) within 5 minutes prior to each PK sample collection pre-infusion and at 30 and 60 minutes post-infusion (see footnote (m) and [Table 6](#)).
- d MUGA or 2-D ECHO to quantify LVEF. Must be completed within 28 days prior to start of first cycle of study drug.
- e To be collected prior to SL-401 infusion if during dosing period. Hematology includes WBC count with differential, RBC count, hematocrit, hemoglobin and platelet count.
- f To be collected prior to SL-401 infusion if during dosing period. Electrolytes include sodium, potassium, bicarbonate, chloride, BUN, creatinine and glucose.
- g To be collected prior to SL-401 infusion if during dosing period. Serum albumin may be a component of the chemistry panel (h). See protocol for administration of albumin if serum albumin decreases to <3.0 g/dL during treatment days or in the immediate post-treatment period.
- h To be collected prior to SL-401 infusion if during dosing period. Serum chemistry includes electrolytes (see above, footnote f) and the following: ALT, albumin, ALP, AST, bilirubin (total, direct, and indirect), calcium, creatine phosphokinase (CPK), magnesium, LDH, phosphate, total protein, and uric acid.
- i To be collected prior to SL-401 infusion if during dosing period. Urinalysis includes appearance, color, pH, specific gravity, ketones, leukocytes, protein, glucose, bilirubin, urobilinogen, and occult blood.
- j Morphology and differential WBC/blast count on aspirate. Baseline must be performed within 14 days prior to the first administration of SL-401. Subsequent bone marrow aspirates (+ biopsy) will be performed at the end of Cycles 2, 4 and 6 and every 3 months (\pm 1 month) thereafter through 12 months after the start of SL-401 and at the Investigator's discretion thereafter. If the end-of- Cycle 2/4/6 bone marrow aspirate (+ biopsy) is empty, hypocellular, or inadequate, a bone marrow examination should be repeated within 14 (\pm 7) days to document response. All bone marrow samples collected on study will be assessed centrally. Bone marrow (2 mL aliquot) will be prioritized for assessment of MRD at the [REDACTED]. Additional bone marrow (~5 mL) is to be aliquoted for tumor assessment and for translational evaluation at MD Anderson Cancer center. CD123 is to be assessed in all bone marrow samples (and, if applicable, tissue samples) by flow cytometry (i.e., CD123 should be added to the panel of markers assessed by flow cytometry of bone marrow aspirates) and immunohistochemistry and the results recorded and captured in the eCRF.
- k Refer to Section [7.5.2](#) – Premedication and Administration.
- l Following treatment with premedication, SL-401 will be administered as a 15-minute infusion for the first 5 consecutive days of a 28-day cycle. Individual SL-401 infusions may be delayed to allow for toxicity resolution; all infusions should be completed within 10 days. Patient must be monitored for 4 hours post infusion.
- m Plasma samples (6 mL each) will be collected immediately prior to the start of the infusion of SL-401, immediately after end of infusion (time recorded), then 15, 30, 45, 60, 90, 120, 180, and 240 minutes after completion of the infusion during infusions 1 (i.e., Study Day 1) and 5 (i.e., Study Day 5) during Cycles 1 & 3 (see (c)).
- n For patients who live a considerable distance from the Study Center, for whom weekly travel to the Study Center is not feasible, the Day 8, 15, and 21 (\pm 3 days) laboratory assessments (blood and urine) may be submitted to a local laboratory, although the results must be evaluated by the Study team. Concomitant medication and AE monitoring on these days will take place via telephone contact. In situations where SL-401 is not administered over 5 consecutive days (i.e., treatment delays because of AEs or other factors) and an infusion is to be administered on Day 8, all pre-infusion/infusion evaluations should be conducted, in addition to concomitant medications recorded. Upon completion of the 5th Cycle 1 infusion (Day 8, 9 or 10), the blood/urine/concomitant medication and AE assessments should be planned for Day 15, as indicated in the table.
- o The end-of-the cycle evaluations (Day 28 or thereafter) may also serve as the pre-infusion evaluations for Cycle 2; these do not need to be duplicated on successive days unless there is an abnormality or other clinically relevant reason for repeat evaluation.

Table 6: Study Events Schedule for Cycles 2-6 and Subsequent Follow-up

Tests and Observations	Cycle 2-6					End of Treatment	Safety: Through 30 Days After Last Infusion	Survival: Every 90 Days After Last Infusion
	Days 1-5 (Up to Day 10 if Infusion(s) Held) SL-401 Treatment		Day 8±3 ^(m) , 15±3 and 21±3	Day 28±3 ⁽ⁿ⁾	Day 28±3, Then Every 7±3 days			
	Pre-Infusion	Infusion		End of Cycle ⁽ⁿ⁾	Delayed End of Cycle for Toxicity Resolution Only if Required			
Concomitant Medications	X		X	X	X		X	
ECOG performance status				X	X	X		
Physical examination				X		X		
Vital signs and weight ^(a)	X	X		X	X	X		
12-lead ECG ^(b)	X	X (Cycle 3; infusions 1 & 5)		X	X			
Hematology ^(c)	X		X	X	X			
Serum electrolytes ^(d)	X		X	X	X			
Serum albumin ^(e)	X		X	X	X			
Serum chemistry ^(f)	X		X	X	X			
Coagulation parameters: PT/INR, aPTT	X		X	X	X			
Urinalysis ^(g)	X (Infusion 1)		X	X	X			
Tumor response assessment: Bone marrow aspiration + biopsy ^(h)				X (Cycle 2, 4, 6)		X ^(h)		
Administration of premeds ⁽ⁱ⁾	X							
SL-401 administration ^(j)		X						
Pharmacokinetic sampling ^(k)	X (Cycle 3; Infusions 1 &5)	X (Cycle 3; Infusions 1 &5)						
Immunogenicity sampling	X (Infusion 1)			X				X ^(l)
Vision assessment			X (day 21)			X		
AE and SAE monitoring	X	X	X	X	X	X	X	
Long-term Follow-up ^(l)						X	X	

a Vital signs should be performed after patient is sitting for 3-5 minutes. If during dosing period, vital signs should be taken immediately prior to infusion, immediately after completion of infusion, and 30, 60, and 240 minutes post-infusion.

- b All patients will have a 12-lead ECG performed at the screening visit and pre-treatment visit, as well as Day 28. Because PK evaluations will only be performed during Cycles 1 & 3, additional ECGs during the minutes/hours following SL-401 infusions are not required for Cycles 2, 4-6.
- c To be collected prior to SL-401 infusion if during dosing period. Hematology includes WBC count with differential, RBC count, hematocrit, hemoglobin and platelet count.
- d To be collected prior to SL-401 infusion if during dosing period. Electrolytes include sodium, potassium, bicarbonate, chloride, BUN, creatinine and glucose.
- e To be collected prior to SL-401 infusion if during dosing period. Serum albumin may be a component of the chemistry panel (f). See protocol for administration of albumin if serum albumin decreases to <3.0 g/dL during treatment days or in the immediate post-treatment period.
- f To be collected prior to SL-401 infusion if during dosing period. Serum chemistry includes electrolytes (see above, footnote d) and the following: ALT, albumin, ALP, AST, bilirubin (total, direct, and indirect), calcium, creatine phosphokinase (CPK), magnesium, LDH, phosphate, total protein, and uric acid.
- g To be collected prior to SL-401 infusion if during dosing period. Urinalysis includes appearance, color, pH, specific gravity, ketones, leukocytes, protein, glucose, bilirubin, urobilinogen, and occult blood.
- h Morphology and differential WBC/blast count on aspirate. Baseline must be performed within 14 days prior to the first administration of SL-401. Subsequent bone marrow aspirates (+ biopsy) will be performed at the end of Cycles 2, 4 and 6 and every 3 months (\pm 1 month) thereafter through 12 months after the start of SL-401 and at the Investigator's discretion thereafter. If the end-of- Cycle 2/4/6 bone marrow aspirate (+ biopsy) is empty, hypocellular, or inadequate, a bone marrow examination should be repeated within 14 (\pm 7) days to document response. All bone marrow samples collected on study will be assessed centrally. Bone marrow (2 mL aliquot) will be prioritized for assessment of MRD at the [REDACTED]. Additional bone marrow (~5 mL) is to be aliquoted for tumor assessment and for translational evaluation at MD Anderson Cancer center. CD123 is to be assessed in all bone marrow samples (and, if applicable, tissue samples) by flow cytometry (i.e., CD123 should be added to the panel of markers assessed by flow cytometry of bone marrow aspirates) and immunohistochemistry and the results recorded and captured in the eCRF.
- i Refer to Section 7.5.2 – Premedication and Administration.
- j Following treatment with premedication, SL-401 will be administered as a 15-minute infusion for the first 5 consecutive days of a 28-day cycle. Individual SL-401 infusions may be delayed to allow for toxicity resolution, all infusions should be completed within 10 days. Patient must be monitored for 4 hours post infusion. (The administration of additional cycles of SL-401 (beyond 6 cycles) may be considered in the setting of MRD eradication, sustained AML remission, or other evidence of sustained anti-leukemia benefit in the opinion of the Investigator. Administration of SL-401 beyond 6 cycles must be discussed with the Medical Monitor at which time the individual patient's potential risk/benefit of further treatment will be assessed).
- k Plasma samples (6 mL each) will be collected immediately prior to the start of the infusion of SL-401, immediately after end of infusion (time recorded), then 15, 30, 45, 60, 90, 120, 180, and 240 minutes after the start of the infusion during infusions 1 (i.e., Day 1) and 5 (i.e., Day 5) of Cycles 1 & 3. PK evaluation will not be performed for Cycles 2, 4-6.
- l After the follow-up visit, patients will then be followed every 90 days for survival status for at least one year following the start of SL-401. The survival follow-up may be by telephone contact. Patients who undergo SCT will be followed for the occurrence of VOD as part of long-term follow-up. A blood sample for immunogenicity studies will be collected at least 16 weeks to up to 20 weeks after the last SL-401 dose.
- m For patients who live a considerable distance from the Study Center, for whom weekly travel to the Study Center is not feasible, the Day 8, 15, and 21 (\pm 3 days) laboratory assessments (blood and urine) may be submitted to a local laboratory, although the results must be evaluated by the Study team. Concomitant medication and AE monitoring on these days will take place via telephone contact. In situations where SL-401 is not administered over 5 consecutive days (i.e., treatment delays because of AEs or other factors) and an infusion is to be administered on Day 8, all pre-infusion/infusion evaluations should be conducted, in addition to concomitant medications recorded. Upon completion of the 5th Cycle 1 infusion (Day 8, 9 or 10), the blood/urine/concomitant medication and AE assessments should be planned for Day 15, as indicated in the table.
- n The end-of-the cycle evaluations (Day 28 or thereafter) may also serve as the pre-infusion evaluations for the subsequent cycles; these do not need to be duplicated on successive days unless there is an abnormality or other clinically relevant reason for repeat evaluation.

Table 7: Time Points for Pharmacokinetic Blood Draws and ECGs

Collection Timepoint	Day			
	Cycles 1 and 3: Day 1/Infusion 1		Cycles 1 and 3: Day 5/Infusion 5	
	ECG	PK	ECG	PK
Pre-Infusion	X	X	X	X
Immediately After End of Infusion (time recorded)		X		X
15 Minutes Post-Infusion		X		X
30 Minutes Post-Infusion	X	X	X	X
45 Minutes Post-Infusion		X		X
60 Minutes Post-Infusion	X	X	X	X
90 Minutes Post-Infusion		X		X
120 Minutes Post-Infusion		X		X
180 Minutes Post-Infusion		X		X
240 Minutes Post-Infusion		X		X

10 Adverse Events and Safety Evaluation

The AE reporting period for a patient treated in the study begins with the initiation of SL-401 and is continuous through 30 days after the last SL-401 infusion. All AEs that occur in treated patients during the AE reporting period specified in the protocol must be reported to the Sponsor, whether or not the event is considered related to SL-401. Any known untoward event that occurs beyond the AE reporting period that the Investigator assesses as related to SL-401 should also be reported as an AE.

All patients should be monitored per institutional guidelines for at least 4 hours following the administration of each infusion of SL-401. The Principal Investigator, who is a physician, or medical staff responsible for study conduct and safety evaluations, should be available during the administration SL-401 and follow-up to assess, treat, or report as necessary any AE or SAE that may occur.

10.1 Definitions

All observed or volunteered AEs regardless of suspected causal relationship to SL-401 will be reported as described below.

10.1.1 Adverse Event (AE)

An AE is any untoward medical occurrence in a study patient who is administered a medicinal product (drug or biologic); the event may or may not have a causal relationship with the medicinal product. Examples of AEs include, but are not limited to, the following:

- Clinically significant symptoms and signs including:
 - Worsening of signs and symptoms of the disease under study; disease progression without worsening of signs and symptoms as assessed by bone marrow aspiration (BMA) or other methods should not be reported as AEs.
 - Signs and symptoms resulting from drug overdose, abuse, misuse, withdrawal, sensitivity, dependency, interaction, or toxicity.
 - All possibly related and unrelated illnesses, including the worsening of a preexisting illness.
 - Injury or accidents. Note that if a medical condition is known to have caused the injury or accident (hip fracture from a fall secondary to dizziness), the medical condition (dizziness) and the outcome of the accident (hip fracture from a fall) should be reported as 2 separate AEs.
- Abnormalities in physiological testing or physical examination findings that require clinical intervention or further investigation (beyond ordering a repeat confirmatory test).
- Laboratory abnormalities that meet any of the following (Note: merely repeating abnormal test, in the absence of any of the below conditions, does not constitute an AE. Any abnormal test result that is determined to be an error does not require reporting as an AE):
 - Test result that is associated with accompanying symptoms
 - Test result that requires additional diagnostic testing or medical/surgical intervention
 - Test result that leads to significant additional concomitant drug treatment or other therapy
 - Test result that is considered to be an AE by the Investigator or Sponsor

Note that VOD occurring post-SCT and any changes in visual acuity and/or color vision will be followed as adverse events of special interest.

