Assessments for safety, efficacy, and biological/correlative effects will be performed according to the schedules outlined in [Table 5](#) and [Table 6](#).

Safety Assessments:

Safety assessments include DLTs, adverse events (AEs), serious adverse events (SAEs), physical examinations, vital sign measurements, clinical laboratory evaluations, and reasons for treatment discontinuation due to toxicity. In addition, patients will be monitored for changes in visual acuity and color vision and post-transplantation veno-occlusive disease (VOD).

The AE reporting period for a patient treated in the study begins with the initiation of SL-401 and is continuous through 30 days after the last SL-401 infusion. All AEs that occur in treated patients during

the AE reporting period specified in the protocol must be reported to the Sponsor, whether or not the event is considered related to SL-401. Any known untoward event that occurs beyond the AE reporting period that the Investigator assesses as related to SL-401 should also be reported as an AE.

Efficacy Assessments:

Efficacy assessments include RFS, OS, and presence of MRD positive cells during follow-up.

Correlative Studies:

Bone marrow samples will be collected to determine the frequencies of leukemia stem cells and MRD positive cells and changes in intracellular signaling upon SL-401 treatment, and for in vivo engraftment studies. All patient samples will be collected at the treatment sites and immediately shipped to the designated central laboratories for analysis.

Pharmacokinetic (PK) Studies:

An intensive schedule for collection of blood samples after specific infusions during Cycles 1 & 3 of SL-401 will be used to determine plasma concentrations of SL-401. Plasma concentration data over time will be used to characterize the PK disposition of SL-401, to assess any change in the PK properties of SL-401 during the 5-day course of treatment, and relate the PK characteristics of SL-401 to toxicity and disease activity. The nominal blood sampling time schedule is summarized in [Table 7](#).

Immunogenicity Studies:

Blood samples will be collected for the detection of SL-401 reactive antibodies.

Cardiac Assessments:

All patients will have 12-lead ECGs performed according to the schedule in [Table 7](#). All ECGs will be analyzed locally.

Statistical Methods:

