4.4.2. Adverse Events

All AEs will be coded using the MedDRA coding system and displayed in tables and data listings using system organ class (SOC) and preferred term (PT).

Analyses of AEs will be performed for those events that are considered treatment-emergent, where treatment-emergent is defined per protocol as any AE with onset after the first administration of Tagraxofusp through 30 days after the last dose of Tagraxofusp, or any event that was present at baseline but worsened in intensity or was subsequently considered drug-related by the Investigator through 30 days after the last dose of Tagraxofusp.

The number and percentage of patients with any treatment-emergent AE (TEAE), with any TEAE assessed by the Investigator as related to treatment, with any TEAE with severity \geq Common Terminology Criteria for Adverse Events (CTCAE) Grade 3, with any SAE, with any AE leading to discontinuation of study treatment, and with any AE leading to dose modification will be summarized by dose group and overall. In these tabulations, each patient will contribute only once (ie, the most related occurrence or the most intense occurrence) to each of the incidence rates in the descriptive analysis, regardless of the number of episodes.

Treatment-emergent AEs summarized by patient incidence rates are not tabulated by severity or relationship to study treatment; therefore, in such tabulations, a patient contributes only once to the count for a given AE SOC or PT. For tabulations that include classification by relationship to study treatment, AEs with missing relationship will be considered related to study drug.

Adverse events of special interest (AESI's) will be determined using MedDRA version 19.0 standardized medical queries (SMQs), high-level terms, or PTs, as follows:

- Possible hypersensitivity events, based on the SMQ Hypersensitivity (broad search).
- Vascular capillary leak syndrome (CLS), based on the MedDRA SMQ [to be provided] in addition to PTs of hypoalbuminaemia, blood albumin decreased, and proteinuria.
- Possible drug-induced liver injury events, based on the SMQ drug-related hepatic disorders (broad search).

Summary tables of AESIs produced will report AESIs as follows:

- AESIs overall and by PT,
- AESIs by PT overall and by grouped cycle (Cycle 1, Cycles 2-4, Cycles \geq 5),
- \geq 3 Grade AESIs overall and by PT,
- Serious AESIs overall and by PT,
- AESIs resulting in drug interruption overall and by PT,

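### The protocol's two adverse events of special interest, post-transplant VOD and vision changes, are not on the SAP's list, and a late VOD would enter no planned table

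*Protocol*

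**What the plan says.** Protocol 10.1.1 closes its definition of an adverse event with a designation: "Note that VOD occurring post-SCT and any changes in visual acuity and/or color vision will be followed as adverse events of special interest". The synopsis repeats both items under Safety Assessments: "patients will be monitored for changes in visual acuity and color vision and post-transplantation veno-occlusive disease (VOD". Protocol 9.7 places the VOD follow-up after treatment: "Patients who undergo SCT will be followed for the occurrence of VOD as part of survival monitoring". That monitoring runs about every 90 days, and footnote l of Protocol Table 6 sets a minimum of one year from the start of SL-401.

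SAP 4.4.2 defines adverse events of special interest (AESIs) by three searches:

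- "Possible hypersensitivity events, based on the SMQ Hypersensitivity (broad search"
- "Vascular capillary leak syndrome (CLS), based on the MedDRA SMQ [to be provided", where the bracket is an unfilled placeholder, followed by three preferred terms
- "Possible drug-induced liver injury events, based on the SMQ drug-related hepatic disorders (broad search"

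The same section sets the scope: "Analyses of AEs will be performed for those events that are considered treatment-emergent". Treatment-emergent means "any AE with onset after the first administration of Tagraxofusp through 30 days after the last dose of Tagraxofusp", or a baseline event that worsened or was later judged drug-related within the same 30 days. Elsewhere in the SAP, VOD occurs only in a copied schedule footnote and vision assessment only as a schedule row.

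**The concern.** Characterising safety is a primary objective. The protocol singled out two kinds of event and gave each its own follow-up. The SAP plans eight AESI summaries, but for a different list.

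For VOD there is a second problem. The follow-up meant to find it runs mainly after the date on which the SAP stops counting events. A programmer who follows the SAP exactly could deliver a full set of safety tables in which a recorded late VOD is not counted. Nor does any planned table use transplanted patients, the only ones at risk of this event, as its denominator.

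**Working it through.** The plan states no figure on this point to reproduce. The check compares the two documents and then does day arithmetic on the window.

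**1. The two lists**

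| Event | Protocol 10.1.1 | SAP 4.4.2 list |
|---|---|---|
| VOD after SCT | AESI | not named |
| Change in visual acuity or color vision | AESI | not named |
| Hypersensitivity | not named there | AESI |
| Capillary leak syndrome | not named there | AESI |
| Drug-induced liver injury | not named there | AESI |

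The lists have no named item in common. The broad hepatic search might pick up VOD, but the SAP does not give its terms, so the documents cannot confirm this. Even if it did, it would not mark the event as post-transplant.

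**2. The window against the VOD follow-up**

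Inputs:

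- Cycles of 28 days, with the last infusion on Day 5, or as late as Day 10 if doses are postponed (Protocol 7.5.2).
- Up to 6 cycles (Protocol 7.5.2).
- Window closing 30 days after the last dose (SAP 4.4.2).
- Follow-up of at least 365 days from the first infusion (Protocol Table 6, footnote l).
- Assumption: cycles start on time.

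Formulas, for c cycles with last infusion on day d of the final cycle:

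- Window end = 28 × (c − 1) + d + 30
- Days outside = 365 − window end

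| Cycles | Window ends (d = 5 to 10) | Days outside, first year | Share of 365 |
|---|---|---|---|
| 1 | Day 35 to 40 | 330 to 325 | 90% to 89% |
| 2 | Day 63 to 68 | 302 to 297 | 83% to 81% |
| 4 | Day 119 to 124 | 246 to 241 | 67% to 66% |
| 6 | Day 175 to 180 | 190 to 185 | 52% to 51% |

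Example: with 6 cycles and d = 10, the window ends on 28 × 5 + 10 + 30 = Day 180, and 365 − 180 = 185 days, or 51%.

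The first scheduled survival contact, about 90 days after end of treatment, also falls after the window. The onset date, not the contact date, decides whether an event counts, so a VOD that began within 30 days but was learned of later is still treatment-emergent.

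**3. Where each event would be reported**

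- *VOD, onset within 30 days of the last dose:* in the general tables by system organ class and preferred term. Not an AESI by name.
- *VOD, onset later:* not treatment-emergent under either branch of the definition. The AESI table by period has Cycle 1, Cycles 2–4 and Cycles ≥5, with no follow-up row. It is in no table, and in a listing if it is on the eCRF (SAP 3.10).
- *Vision change within 30 days, reported as an adverse event:* in the general tables, without an AESI grouping.
- *Exception:* SAP 3.10 sets a wholly missing onset date to the first day of treatment, so a VOD record without a date would be counted.

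**The case against.** The best defence is that the SAP follows the protocol's analysis section. Protocol 11.4 itself summarises events through 30 days after the last infusion and plans no AESI table. Section 10.1.1 says the two events will be followed as AESIs, which is a commitment to monitor. This stands, and it limits the point. A reader might infer from SAP section 5, which declares no changes from the protocol-defined analyses, that the declaration is false. On this matter it is not: no analysis defined in the protocol was dropped. The mismatch is between the protocol's designation and follow-up (10.1.1 and 9.7) and the analysis sections of both documents.

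The second defence is that nothing is hidden. SAP 3.10 puts all eCRF data into listings, and 27 patients were enrolled by database lock (18 in Stage 1, 9 in Stage 2; SAP 3.1), so a recorded VOD could be found by reading them. This also stands. A reader might conclude that the study report would show no VOD at all; the documents support only that no table would count a late one.

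Third, the issue may never arise. Inclusion criterion 6 admits patients who are not immediate candidates for allogeneic transplant. A reader might infer that transplant after treatment is expected, because SAP 4.3.2 has a relapse-free survival rule for it and Protocol 9.7 follows transplanted patients. Those provisions show that transplant is allowed for, not that it is expected.

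None of this supplies a table for a late VOD, or a grouping for either protocol AESI.

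**Conclusion.** The point holds in limited form. Neither protocol AESI is named in the SAP list, and a post-transplant VOD with onset more than 30 days after the last dose has no planned table. For vision changes within 30 days the gap is smaller: only the AESI grouping is missing.

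The effect on the results cannot be sized. The documents give no number of transplants and no number of VOD cases, and either may be zero. A reader might want to express one missed case as a rate among transplanted patients, but any such figure would rest on an invented denominator. The 51% to 90% describes follow-up time outside the window, assumes undelayed cycles, and says nothing about risk.

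The conclusion rests on reading the treatment-emergent limit at the head of SAP 4.4.2 as governing the AESI tables below it. If it did not govern them, VOD would still be unnamed in the list. The change is worth making because the gap touches a primary safety objective and is cheap to close.

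**What to change.** In SAP 4.4.2:

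1. Add post-transplant VOD and changes in visual acuity or color vision to the AESI list, each with named MedDRA search terms. The paragraph already needs an edit to fill the capillary leak placeholder.
2. Add one table of post-transplant VOD over all follow-up, regardless of time since the last dose, with the number of patients who had SCT on study as denominator. Print that number even if no VOD occurred.

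The general 30-day tables can stay as they are. A separate table of other late serious or drug-related events is optional.

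The cost is some SAP wording and one small table, with no change to patient procedures. The table can show only late VOD that reached the eCRF. Protocol 10.2 collects serious and drug-related events throughout follow-up, but the documents do not say which form would hold a late VOD that is neither. A table footnote should state that limit.
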